APPROVED BY SALUS IRB: 07 MAY 2024

TITLE: Comparative Study of the DMM and Conventional Toric Marker

PROTOCOL NO: IIT# 92162521

AMENDMENT NO: Version 1.0

IRB: Salus IRB
[name]
[name]

SPONSOR: [name] '[name]

INVESTIGATOR: [name] MD
[name]
[name]
United States

**STUDY-RELATED
[contact] (During business hours)
[contact] (24-Hour line)

1. Executive Summary

NEED

There is currently a paucity of data comparing ARGOS combined with the Digital Marker Microscope and other Conventional Marking Modalities for Toric IOL alignment during cataract surgery.

STUDY OBJECTIVE

To evaluate the postoperative refractive accuracy of the common toric Intraoperative marking method of Toric CAM and Mendez marking when compared to ARGOS combined with the Digital Marker Microscope (DMM)/Vision Suite.

STUDY HYPOTHESIS

The DMM linked to Argos preoperative measurements with limbal registration determines the angle for toric IOL alignment intraoperatively more accurately than the manual Mendez marker.

SUPPORTS CLINICAL MESSAGE

The use of ARGOS with intraoperative image guidance improves the toric alignment error significantly and allows for more % of eyes within 0.5D residual CYL (20% more eyes) as compared to manual marking.

STUDY DESIGN

Sample size	35 eyes
Endpoints	
Primary: Difference in intraoperative axis marks with Mendez marker, in degrees and direction, when compared to the DMM as viewed in the intraoperative heads-up display
 
Secondary: % of eyes less than 0.25, 0.5, 0.75, 1.00 and 1.25 D of residual refractive cylinder (CYL) in each group at 1 month postoperatively

Design:	Single-site, head to head, prospective, interventional (all eyes will be planned/implanted using ARGOS with image guidance axis; and the manual marker results will be back calculated utilizing IOL position and post-operative refraction)
DURATION/FOLLOW-UP:	Preoperative to 1 month postoperative

This study will be registered with clinicaltrials.gov. The study will be conducted in compliance with the protocol, GCP, and applicable regulatory requirements.

2. Study Background

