5.3 Postoperative Visits

Subjects will undergo all routine, usual standard-of-care postoperative procedures and follow up appointments.

In addition, 4 weeks following cataract surgery, the final position of the IOL will be confirmed using a slit lamp photograph compared to the ORIGINAL Argos reference image. The surgeon will confirm that the IOL is within 2 degrees of the final intended axis as calculated by the Alcon Vision Planner.

Then the postoperative subjective refraction shall be measured by Snellen and Phoropter method and the theoretical refraction shall be back calculated using the double vector method to arrive with the refraction that would have been obtained by the Mendez marking

method. This will be calculated using the IOL position and post operative refraction with Astigmatismfix.com calculator or equivalent calculation.

6. Statistical Analysis

A summary of the data will be prepared for all measurements. For variables measured on a continuous scale, these summaries will include the sample size, as well as the mean, standard deviation, median, minimum, and maximum. For variables measured on a categorical scale, summaries will provide the number and percentage of eyes in each category. These summaries will be provided for all eyes completing the study.

The statistical analyses will be performed using R, version 4.2.2 or higher. Any statistical tests of hypotheses will employ a level of significance of alpha=0.05.

The primary endpoint will be compared using the paired t-Test. Secondary endpoints will be compared using McNemar's test. Analysis will follow a step down approach:

- Difference in intraoperative axis marks with Mendez marker, in degrees and direction, when compared to the DMM viewed in the intraoperative HUD
- % of eyes less than 0.5D CYL in each group
- % of eyes less than 0.25D CYL in each group
- % of eyes less than 0.75D CYL in each group
- % of eyes less than 1.0D CYL in each group
- % of eyes less than 1.25D CYL in each group

7. Sample Size Justification

Based on the primary endpoint, the study would require a sample size of 21 pairs (to achieve a power of 80% and a level of significance of 5% (two sided), for detecting a mean of the differences of 4.4 between pairs, assuming the standard deviation of the differences to be 6.5.¹

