However, in order to achieve a sample size that allows for statistical analysis of the secondary endpoints, we estimate the sample size required for detecting a difference of 0.20 between the percentage of with postoperative residual astigmatism 0.5 D or less (85% compared to 65%), power of 85%, correlation between paired observations 0.80, and a two-sided significance of 5% is 30.²

To account for dropout, the sample size will be increased to 35 eyes.

References

1. Lipsky L, et al. Comparison of toric intraocular lens alignment error with different toric markers. *J Cataract Refract Surg.* 2019; 45:1597–1601.

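### Section 7 gives 85% power for the 0.5 D comparison as if it were tested alone; under the Section 6 step-down order the chance of that claim is about 80–81% on the plan's own figures

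*Combined protocol and SAP*

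**What the plan says.** Section 6 (Statistical Analysis) fixes the tests: "The primary endpoint will be compared using the paired t-Test. Secondary endpoints will be compared using McNemar's test". It sets the error rate: "Any statistical tests of hypotheses will employ a level of significance of alpha=0.05". It then says "Analysis will follow a step down approach" and lists six items. The first is "Difference in intraoperative axis marks with Mendez marker, in degrees and direction, when compared to the DMM viewed in the intraoperative HUD". The second is the percentage "of eyes less than 0.5D CYL in each group". Four further cylinder cut-offs follow. No stopping rule is written out, but the term step-down implies that a later item is claimed only if the earlier ones succeed.

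Section 7 (Sample Size Justification) first sizes the axis comparison: "the study would require a sample size of 21 pairs (to achieve a power of 80% and a level of significance of 5% (two sided". The inputs are a mean difference of 4.4 and an SD of 6.5. It then raises the number "in order to achieve a sample size that allows for statistical analysis of the secondary endpoints". For 85% against 65% of eyes within 0.5 D, a paired correlation of 0.80, 85% power and a two-sided 5% level, it gives 30. Dropout takes this to 35. No probability of passing both steps appears.

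In Section 1 the axis difference is the primary endpoint and residual cylinder the secondary. The hypothesis there concerns the accuracy of the angle. The objective is worded in refractive terms: "To evaluate the postoperative refractive accuracy of the common toric Intraoperative marking method of Toric CAM and Mendez marking" against the digital system.

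**The concern.** The 0.5 D comparison sets the enrolment and is the endpoint closest to the stated objective. A reader of Section 7 will take 85% as the chance that the study can claim a difference on it, if the assumed rates are true. Under a step-down rule it is not. The axis-mark test must succeed first, so the relevant quantity is the probability of passing both.

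The two steps also respond to different features of the data. If the t-test uses signed differences, as recording direction suggests, it responds to the average rotation, and clockwise and counterclockwise errors cancel. Back-calculated cylinder responds to the size of each eye's misalignment, which does not cancel. The chance of reaching the second step therefore rests on an assumption that Section 7 makes only for the first: a mean rotation well away from zero.

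**Working it through.** **Inputs.** All are from Sections 6 and 7: mean 4.4 and SD 6.5 degrees; two-sided 5%; 85% and 65% within 0.5 D; correlation 0.80; power 85%; 30 pairs, raised to 35.

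**1. The plan's figures.**
- *Axis test.* Noncentral t with noncentrality (4.4/6.5)·√n. Power is 81.9% at n = 20 and 83.9% at n = 21, so the stated 21 pairs for 80% is adequate.
- *0.5 D test.* The proportion within 0.5 D by both methods is p11 = 0.85·0.65 + 0.80·√(0.85·0.15·0.65·0.35) = 0.5525 + 0.80·0.1703 = 0.6887. The discordant proportion is 0.85 + 0.65 − 2·0.6887 = 0.1225. Then n = [1.960·√0.1225 + 1.036·√(0.1225 − 0.04)]²/0.04 = 24.2, or 25 pairs; a continuity-corrected formula gives 29. The stated 30 is close to the latter.

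**2. First step at the planned size.** At n = 30 the noncentrality is 0.6769·5.477 = 3.71, and power is 94.8%. At n = 35 it is 97.3%.

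**3. Both steps, taking 85% at face value.**
- n = 30, independent steps: 0.948 × 0.85 = 80.5%. For any dependence, the lower bound is 0.948 + 0.85 − 1 = 79.8% and the upper bound is 85%.
- n = 35, second step held at 85%: 0.973 × 0.85 = 82.7%.

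**4. Dependence on mean rotation, signed test.** Hold the overall size of the differences at the plan's value, √(4.4² + 6.5²) = 7.85 degrees, and change only the mean. The SD is then √(61.61 − mean²).

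| Mean (degrees) | SD | First step succeeds, n = 30 |
|---|---|---|
| 4.4 | 6.50 | 94.8% |
| 3 | 7.25 | 59.1% |
| 2 | 7.59 | 28.7% |
| 1 | 7.79 | 10.5% |
| 0 | 7.85 | 5.0% |

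With the SD held at 6.5 instead, the figure at a mean of 2 is 37.1%. If absolute differences are tested against zero, a simulation of normal differences with the same overall size passes the first step in essentially every trial at means of 4.4, 2 and 0.

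**5. Feasibility of the 85% base.** p11 cannot exceed the smaller rate, 0.65, but correlation 0.80 requires 0.6887. The largest possible correlation is (0.65 − 0.5525)/0.1703 = 0.57. There, 20% of eyes are discordant, all favouring the digital method. Uncorrected McNemar then rejects with 4 or more discordant eyes; the exact or continuity-corrected version needs 6 or more. Binomial power and the product with step 2:

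| n | McNemar version | Second step alone | Both steps (independent) |
|---|---|---|---|
| 30 | Uncorrected | 87.7% | 83.1% |
| 30 | Exact or corrected | 57.2% | 54.3% |
| 35 | Uncorrected | 93.9% | 91.4% |
| 35 | Exact or corrected | 72.8% | 70.8% |

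These are best cases for correlation. At correlation 0.5 and n = 30, the second step alone has 74.7% (uncorrected) or 52.1% (exact).

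**The case against.** Placing the declared primary endpoint first is ordinary practice, and it matches the angle-accuracy hypothesis in Section 1. Quoting a secondary endpoint's own power is also common. On the plan's own axis assumptions the gap is about 4 to 5 points at 30 eyes and about 2 at 35. All of this stands, and it makes the point a modest one. It does not make 85% the chance of a claim under the order in Section 6.

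Two stronger readings are tempting.

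A reader might infer that the chance of a 0.5 D claim collapses to about 4%. That is 0.05 × 0.85. It requires a signed t-test, a true mean rotation of exactly zero, and roughly independent steps. The plan assumes 4.4 degrees, and Section 6 does not say whether signed or absolute differences are tested. The figure is an extreme of an undefined test, not a consequence of the order alone.

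A reader might also infer that the 0.5 D test should come first. The documents do not support that either. It would put a secondary endpoint ahead of the one declared primary and cap the primary's chance of a claim at the 0.5 D test's own power. That cap is at best 87.7% at n = 30, and 57.2% with the exact test, against 94.8% now. In a vector simulation matching 85% against 65%, the 0.5 D test's own power is about 59%, or about 44% with continuity correction. That run assumes 1.25 D of lens cylinder at the refraction plane and an isotropic residual, neither of which is in the documents.

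Finally, the stopping rule is inferred. If the list were only a reporting order, the joint probability would not apply, but the sequence would then not control the error rate across its six tests.

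**Conclusion.** The point holds as a minor, wrong-as-written figure. The 85% in Section 7 is the stand-alone power of the second step. Under the order in Section 6, with the plan's 4.4 and 6.5 degrees, 30 evaluable eyes and 85% at face value, the chance of a 0.5 D claim is about 80–81% (bounds 80% to 85%). It is about 83% with all 35 eyes and the second step held at 85%.

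Two conditions limit what any single replacement figure can say. With signed differences, it depends on the assumed mean rotation: the first step succeeds about 29% of the time at 2 degrees and 5% at zero, with the overall size of the differences held fixed. With absolute differences this loss disappears. And the 85% base rests on a correlation that cannot occur with the stated rates, so the choice of McNemar version matters more than the order of testing does under the plan's axis assumptions.

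**What to change.** Keep the axis-mark difference first. In Section 7, label 85% as the stand-alone power of the second step and add the probability of passing both steps. Compute it from a paired correlation compatible with 85% and 65% (at most about 0.57) and from the McNemar version to be used, and name both. State that the probability depends on the assumed mean signed rotation, with values at one or two smaller means. For the calculation to be defined, Section 6 should say in one sentence each whether the t-test uses signed or absolute differences, and that testing stops at the first non-significant item.

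The cost is amendment wording in Sections 6 and 7, settled before the data are analysed. This change alone requires no more eyes. The downside is a less favourable figure at 30 eyes: about 81% on the plan's own inputs, and about 83% (uncorrected) or 54% (exact or corrected) at the largest feasible correlation. The sponsor may then wish to revisit the number of eyes, which is a separate decision.

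### The first-ranked secondary endpoint is tested as less than 0.5 D but powered as 0.5 D or less, and the two cylinder values are not put on one scale

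*Combined protocol and SAP*

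**What the plan says.** The limit is worded differently in four places:

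| Place | Wording | Limit |
|---|---|---|
| Section 1, endpoint row | percentage "of eyes less than 0.25, 0.5, 0.75, 1.00 and 1.25 D of residual refractive cylinder (CYL) in each group" | strict (<) |
| Section 6, test list, first secondary endpoint | percentage "of eyes less than 0.5D CYL in each group" | strict (<) |
| Section 7, sample size | "postoperative residual astigmatism 0.5 D or less (85% compared to 65"%) | inclusive (≤) |
| Section 1, clinical message | "allows for more % of eyes within 0.5D residual CYL (20% more eyes) as compared to manual marking" | usually read as inclusive; its 20% matches Section 7's difference |

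The two values compared in each eye also have different origins. Section 5.3 has the postoperative refraction "measured by Snellen and Phoropter method and the theoretical refraction shall be back calculated using the double vector method". The DMM value is therefore measured, and the Mendez value is derived from it. On the tool, Section 5.3 says: "This will be calculated using the IOL position and post operative refraction with Astigmatismfix.com calculator or equivalent calculation". Sections 3, 5.3 and 6 give no recording step, number of decimals, rounding rule or rule for an eye at exactly 0.50 D.

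**The concern.** This endpoint sets the size of the trial. The primary endpoint needs 21 pairs; this one raises the number to 30 and then 35. If its limit is strict in the test and inclusive in the power calculation, the protocol states no power for the test that will be run.

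The missing resolution makes the choice of word more important. McNemar's test uses only the eyes that the two methods classify differently. If one value moves in steps and the other does not, an eye at exactly 0.50 D on the stepped scale fails < and passes ≤, while the calculated value rarely lands on 0.50 D. The strict limit then works against DMM and the inclusive one works for it, even when the two axes agree. An analyst who settles the wording after seeing results could decide the clinical message.

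**Working it through.** **1. The plan's own figure.** Inputs from Section 7: 85% and 65%, correlation 0.80, power 85%, two-sided 5%. McNemar size by Connor's formula:

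- p11 = 0.85×0.65 + 0.80×√(0.85×0.15×0.65×0.35) = 0.5525 + 0.1362 = 0.6887
- discordant share pd = 0.85 + 0.65 − 2×0.6887 = 0.1225; d = 0.20
- n = [1.960×√0.1225 + 1.036×√(0.1225 − 0.04)]² / 0.04 = 24.19
- with continuity correction 1/d: 24.19 + 5 = 29.19, rounded up to **30**

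The 30 is reproduced, and it rests on the inclusive rates.

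**2. Eyes on the boundary.** Assumptions not in the documents: 0.25 D refraction steps and bivariate normal residual astigmatism with component SD σ. A recorded value of 0.50 D or less then means a true value below 0.625 D.

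- 1 − exp(−0.625²/2σ²) = 0.85 gives σ = 0.321 D
- strict rate: 1 − exp(−0.375²/2σ²) = 0.495
- share at exactly 0.50 D: 0.850 − 0.495 = **35%** of DMM eyes

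**3. Effect on the test.** Simulation with 35 eyes: the Mendez vector is the recorded vector plus C×(1 − e^(2iδ)), where C is the toric effect. The marking difference δ has mean 4.4 and SD 6.5 degrees (Section 7), in whole degrees. McNemar's test is continuity-corrected. C is an assumption, solved so that Mendez gives 65% for ≤: 1.55 D if both values share one 0.25 D grid, 0.63 D if the Mendez value is unrounded.

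| Case | Rates ≤ (DMM vs Mendez) | Significant, ≤ | Significant, < |
|---|---|---|---|
| 1.55 D, one grid | 85% vs 65% | DMM 57% | DMM 34% (rates 50% vs 33%) |
| 1.55 D, Mendez unrounded | 85% vs 50% | DMM 97% | DMM 1.6% |
| 0.63 D, Mendez unrounded | 85% vs 65% | DMM 71% | **Mendez** 31% |
| 0.63 D, one grid | 85% vs 81% | DMM 1% | DMM 2% |

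**4. Eyes for 85% power, 1.55 D on one grid.** Discordant rates are 22.9% and 2.8% for ≤, and 23.6% and 6.6% for <.

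- ≤: pd = 0.257, d = 0.201; the formula in step 1 gives 53.9 + 1/0.201 = 58.9, so 59
- <: pd = 0.302, d = 0.170; it gives 90.7 + 1/0.170 = 96.5, so 97

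The corresponding power calculation for the continuity-corrected test gives about 58 and 98.

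**5. The artefact by itself.** With almost no marking difference (mean 0, SD 1 degree; 1.55 D), one grid gives 0% significant results for either limit. With the Mendez value unrounded, ≤ declares DMM better in 20% of trials and < declares Mendez better in 15%.

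**6. Range.** On one grid the better limit for power depends on inputs the documents do not give. For ≤ versus <: 7.5% vs 66% at SD 0.20 D and toric 1.0 D; 59% vs 40% at SD 0.30 D and 1.5 D; 88% vs 62% at SD 0.30 D and 2.0 D. With 0.125 D steps, retuned on one grid, the figures are 56% vs 48% on one grid and 85% vs 16% unrounded.

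**7. Other cut-offs, 1.55 D.** About 42% of DMM eyes sit at exactly 0.25 D. On one grid the strict 0.25 D endpoint counts only eyes recorded as 0.00 D (7% vs 4%) and is significant for DMM in 0.5% of trials, against 34% for ≤. About 13% of DMM eyes sit on 0.75 D, 2% on 1.00 D and almost none on 1.25 D.

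**The case against.** The wording conflict is not in dispute; its weight is.

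- **The 85% power fails for ≤ as well.** With 85% and 65% the correlation cannot exceed 0.572, so 0.80 is impossible. That is why the ≤ case on one grid reaches only 57%. This stands as a separate defect. It should not be charged to the boundary word; the effect of the word is the gap between 57% and 34%.
- **The word alone may leave the size unchanged.** If the difference stays at 20 points and the correlation is at its feasible maximum, the discordant share is 0.20 for either limit, and step 1's formula gives 42 eyes uncorrected or 47 corrected. This is true, but it requires equal shares of both groups at exactly 0.50 D. If 20% of DMM eyes and 10% of Mendez eyes sit there, 85% vs 65% becomes 65% vs 55%, and the difference halves.
- **The step, residual SD, toric effect and calculator precision are assumed.** This stands. If the calculator reports in the refraction's step, the scale artefact disappears. If neither value is stepped, the word makes no practical difference.
- **The 97% figure is off-plan.** Its Mendez rate is 50%, not 65%. Reversal is mainly a low-toric result: Mendez is favoured under < in about 1% of trials at 1.55 D, 9% at 1.0 D and 31% at 0.63 D.
- **The 4.4 may not be a signed mean.** With mean 0, the 1.55 D one-grid case falls to 35% vs about 23%, and reversal at 0.63 D rises to about 38%. The sizes move, but the problem remains.
- **The clinical message is not an endpoint definition.** Agreed. The conflict with Section 7 does not need it.

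**Conclusion.** The concern holds and should be fixed. The protocol tests one endpoint and powers another, which follows from the text without any assumption. It also leaves a measured and a calculated cylinder without a common resolution, so the boundary word may decide the result.

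Confidence is high on the contradiction and moderate on its consequence. Under 0.25 D steps and the tuned model, the word moves the chance of a significant DMM result from 57% to 34% on a shared grid. On mismatched scales it can move it from near-certain to near zero, or reverse the direction. Neither limit is uniformly more powerful.

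The primary endpoint is unaffected. Section 6 says "Analysis will follow a step down approach" but does not say whether a non-significant result stops later tests. Only if it does would this problem reach the remaining cut-offs through the order.

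**What to change.** Make two changes together, before results are seen.

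1. **One boundary** in Sections 1, 6 and 7, for all five cut-offs. The inclusive limit matches Section 7's rates and the clinical message. The strict limit is also coherent, but Section 7's rates, power and number of eyes must then be restated for it.
2. **One resolution.** State the step in which the refraction is recorded and classify both values at that step, for example by rounding the back-calculated cylinder to it.

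The inclusive limit without a common resolution would favour DMM, so the first change should not be made alone.

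The cost is a few words in Sections 1, 5.3, 6 or 7, and no extra data if the inclusive limit is kept. Rounding discards some information. Depending on residual error and toric power, ≤ on a common grid may have less or more power than <, as the range in the working shows. Keeping the strict limit may need more eyes. The infeasible correlation in Section 7 needs its own correction whichever limit is chosen.

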Toric IOLs offer patients with corneal astigmatism, increased spectacle independence after cataract surgery. Toric marking aims at improving the accuracy of incision location and IOL alignment. Conventional markers rely on a reference mark tied to gravitational alignment and the accuracy in manual marking methods is affected by head position, errors on marking and smearing of ink. Digital marking methods aim to reduce intraoperative IOL misalignment using images captured in the sitting position which are used as overlay for IOL alignment intraoperatively¹. The DMM linked to ARGOS preoperative measurements with limbal registration determines the exact angle for toric IOL alignment intraoperatively.

The purpose of this study is to compare the outcome of toric IOL implantation guided by manual or digital marking techniques. The intrinsic difference in the toric axis alignment may lead to a significant difference in the marked alignment axis intraoperatively resulting in superior refractive outcomes and less residual astigmatism using intraoperative alignment from the ARGOS Vision planner and DMM.

3. Study Design

- A single site, interventional study comparing the ARGOS/ DMM axis to the Mendez toric marker paired with the toriCAM smart phone app.
- There will be 35 eyes total that meet the inclusion criteria. Patient's refraction will be evaluated 4 weeks after cataract surgery with a monofocal toric IOL (Clareon Toric).
- Intraoperative difference in toric marks will be recorded in degrees and direction of marking difference (clockwise and counterclockwise).
- Post operative refraction will be obtained at 4 weeks after surgery using standard Snellen acuity chart and phoropter. IOL position will be verified with slit lamp photography aligned with preoperative Argos toric imaging to ensure that IOL position is NOT a source of refractive error.
- We will perform back calculation of theoretical refraction, as if the IOL was positioned at Mendez marking axis rather than the Argos axis. This will be calculated using the IOL position and post operative refraction with Astigmatismfix.com calculator or equivalent calculator

4. Study Inclusion and Exclusion Criteria

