4.2 Exclusion Criteria

If any of the following exclusion criteria are applicable to the subject, the subject should not be included in the study:

- History of amblyopia, macular disease, glaucoma, corneal disease, prior corneal surgery, or diabetes
- IOL final position greater than 2 degrees from intended axis.
- Ocular comorbidity that might hamper post operative visual acuity
- Previous ocular or refractive surgery
- Expected post-op VA worse than 20/25 (Snellen)
- Irregular corneal astigmatism and keratoconus
- Difficulties comprehending written or spoken English language
- Patients that are unable to fixate due to physical or intellectual disability (e.g. Down's Syndrome, Parkinson's Disease)
- Severe/uncontrolled Ocular surface disease/Dry Eye Disease
- Intraoperative complications during procedure

5. Study Procedures

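### The correlation of 0.80 behind the 30-eye calculation is impossible with 85% vs 65% if read as phi, and with 30 evaluable eyes the stated 85% power holds only in a near-boundary case with the uncorrected McNemar test

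*Combined protocol and SAP*

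**What the plan says.** Section 7 first derives 21 pairs for the primary endpoint. It then sizes the study for the secondary endpoints, taking the rate of eyes with "postoperative residual astigmatism 0.5 D or less (85% compared to 65" percent, a difference of 0.20. The remaining inputs and the result are "power of 85%, correlation between paired observations 0.80, and a two-sided significance of 5% is 30". The section continues: "To account for dropout, the sample size will be increased to 35 eyes".

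Section 6 says "Secondary endpoints will be compared using McNemar"'s test and "The statistical analyses will be performed using R, version 4.2.2 or higher". It does not say whether the test is exact, mid-p, continuity-corrected or uncorrected. Section 7 does not define the correlation, name the sample-size formula or give discordant-pair proportions.

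Section 4.2 excludes eyes with "IOL final position greater than 2 degrees from intended axis", which is known only after surgery.

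**The concern.** Each eye gives two yes/no results: within 0.5 D at the DMM axis (observed) and within 0.5 D at the Mendez axis (back-calculated). McNemar's test uses only the eyes in which the two results differ. Once the two rates are fixed, a correlation determines how many such eyes there are. The higher the correlation, the fewer the discordant eyes and the smaller the calculated sample. Two rates 20 points apart need at least 20% discordant eyes, so the correlation has a ceiling well below 1. A value of 0.80 looked too high.

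This calculation, not the primary one, moved the plan from 21 pairs to 30 evaluable and 35 enrolled eyes. The 0.5 D comparison is the first secondary test in the step-down order, and the executive summary builds its clinical message on it. If the input is infeasible, the 85% power has no basis, and a non-significant result could be taken as evidence against a benefit the study was poorly placed to detect.

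**Working it through.** **Inputs (section 7).** p1 = 0.85 (DMM), p2 = 0.65 (Mendez), d = 0.20, two-sided alpha 5%, power 85%, correlation 0.80, n = 30, enrolled 35. The test is McNemar's (section 6). Write p11 for within 0.5 D under both methods, p10 for DMM only, and p01 for Mendez only.

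**1. Reproducing the 30.** With 0.80 as phi and no feasibility check:

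- s = sqrt(0.85 × 0.15 × 0.65 × 0.35) = 0.1703
- p11 = 0.85 × 0.65 + 0.80 × 0.1703 = 0.6887
- p10 = 0.85 − 0.6887 = 0.1613
- p01 = 0.65 − 0.6887 = −0.0387
- total discordance pd = 0.1225
- n = (1.96 × sqrt(pd) + 1.036 × sqrt(pd − 0.04))² / 0.04 = 24.19
- continuity-corrected: n + 1/0.20 = 29.19, or n/4 × (1 + sqrt(1 + 2/(0.20n)))² = 28.98

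That is 29 to 30 eyes. The plan names no formula, so this route to 30 is an inference. Other formulas given 0.80 return values from 19 to 34.

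**2. Feasibility.** p11 cannot exceed 0.65, so phi is at most (0.65 − 0.5525)/0.1703 = 0.0975/0.1703 = 0.572. At 0.80 one cell is negative, and total discordance (0.1225) is below the difference it must contain (0.20). No 2×2 table fits. At the feasible limit (pd = 0.20) the same corrected formulas give 46.67 and 46.54, about 47 eyes. They are approximate; by enumeration the exact or continuity-corrected test needs 41 eyes there.

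**3. Power in the best feasible case (p10 = 0.20, p01 = 0).** Every discordant eye favours DMM, so power is the chance of enough discordant eyes, m:

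- exact: 2 × 0.5^m ≤ 0.05 needs m ≥ 6; continuity-corrected: (m − 1)²/m ≥ 3.84 also needs m ≥ 6
- mid-p: 0.5^m ≤ 0.05 needs m ≥ 5
- uncorrected: m ≥ 3.84 needs m ≥ 4

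With m distributed Bin(30, 0.20), the probabilities are 0.572, 0.745 and 0.877. With 35 eyes they are 0.728, 0.857 and 0.939.

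**4. Other feasible cases.** Power by full trinomial enumeration, two-sided 5%, 30 / 35 evaluable eyes:

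| Case | p10, p01 | Exact or corrected | Mid-p | Uncorrected |
|---|---|---|---|---|
| Best case, phi 0.572 | 0.200, 0 | 57% / 73% | 74% / 86% | 88% / 94% |
| 1% better under Mendez, phi 0.51 | 0.210, 0.010 | 53% / 67% | 69% / 79% | 77% / 83% |
| Tetrachoric 0.80, phi 0.48 | 0.216, 0.016 | 51% / 63% | 66% / 75% | 72% / 79% |
| Phi 0.4 (illustrative assumption) | 0.229, 0.029 | 46% / 57% | 59% / 68% | 62% / 69% |

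**5. Where 85% is reached** (phi scanned from 0.40 to 0.572 in steps of 0.0005):

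- 30 eyes: only uncorrected, from phi 0.5595 (p01 at most 0.22%)
- 35 eyes: uncorrected from phi 0.524 (p01 at most 0.83%); mid-p from phi 0.5675 (p01 at most 0.08%); exact or corrected never

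**The case against.** The strongest defence is that the impossibility depends on reading 0.80 as phi, which the plan does not say. If 0.80 means the share of eyes with the same result under both methods, discordance is 0.20. All inputs are then coherent, and 30 eyes give 88% power with the uncorrected test. That test is a legitimate choice: enumeration puts its type I error at 30 eyes at 4.8% (null discordance 20%) and 4.5% (25%). The endpoint is also secondary, and if all 35 eyes were evaluable the uncorrected power would be 94% in that case.

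Part of this stands. The certain defect is an undefined input; infeasibility follows on the most natural reading of a correlation between paired observations. But agreement of 0.80 with rates 20 points apart is exactly the boundary table, in which no eye does better under Mendez. The plan neither states nor justifies that, and the uncorrected test is not specified. The five extra eyes are a dropout allowance, and section 4.2 can also remove eyes after surgery, so they cannot be counted as spare power.

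A fair caution concerns how likely eyes better under Mendez are. Section 3 says "Intraoperative difference in toric marks will be recorded in degrees and direction of marking difference (clockwise and counterclockwise"), but a rotation in either direction does not show that any eye crosses 0.5 D in Mendez's favour. It only leaves that possible. The plan also assumes that 15% of eyes miss 0.5 D at the DMM axis even though lenses more than 2 degrees off are excluded, so other sources of error must remain. The documents give no rate for such eyes. The limits in step 5 are finer than anyone could forecast: 0.22% of 30 eyes is 0.07 of an eye. They show how narrow the margin is and are not planning values.

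**Conclusion.** The concern holds. The 0.80 is not feasible as phi with these rates, and no reading considered supports 85% power at 30 evaluable eyes except the boundary case, or very near it, combined with the uncorrected test. Exact or continuity-corrected power at 30 eyes is at most 57%, and mid-p at most 74%. Under the tetrachoric reading the range is 51% to 72%.

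These figures rest on the plan's own 85% and 65%, one pair per eye treated as independent, and a two-sided 5% test. The inferred sample-size formula plays no part in them.

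The consequence is limited: the 21-pair primary calculation, the step-down order and the estimates are unaffected. It should still be fixed, because this calculation set the enrolled number and the stated power will frame how the first secondary result is read.

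**What to change.** In section 7, replace the 0.80 with the two discordant-pair proportions the sponsor expects: eyes within 0.5 D only under DMM, and eyes within 0.5 D only under Mendez. They must differ by 20 points, and each needs a justification. Total discordance of 20% to 26% could illustrate the range, but it is an assumption and not from the documents; 20% is the extreme in which no eye does better under Mendez.

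In section 6, name the McNemar version (exact, mid-p, continuity-corrected or uncorrected) before results are seen; naming the software does not settle it. Then restate the power for that version at 30 and 35 evaluable eyes.

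The cost is wording in two sections of an IRB-approved document. Eyes, visits, endpoints and test order stay as they are. The drawback for the sponsor is a less favourable stated power for this endpoint.
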